3.5 Planned Analyses

The analysis of study outcomes will be conducted once all enrolled subjects have been exited from the study. At this time, analyses of the above hypotheses for the primary and secondary endpoints will be performed, and subgroups of interest will also be investigated, tabulated and reported.

3.6 Sample Size and Power

The study sample size (N) is predicated on primary endpoint as detailed above. For the analysis, primary endpoint as well as the secondary endpoints will be tested on the ITT & PP populations. Estimates of effect size for the various outcomes are shown below. Assuming the same effect sizes observed in PROSPECT (clinicaltrials.gov NCT03597100), at $p = 0.01$ we have the following results:

Metric	p value	N
Kinematic measurements for study duration of 2 weeks	0.01	40
Kinematic measurements for study duration of 4 weeks	0.01	30

Under these effect sizes, assuming up to 10% data attrition and with a paired difference test at 0.01 alpha against the null hypothesis of no change from baseline, the 34 to 50 subject analysis provides 90% power for testing of the primary endpoint.

3.7 Subject Disposition and Accountability

Subject disposition will be presented in a table and flow diagram depicting the disposition of all enrolled subjects, including the number enrolled, the number who completed the study and the number and reasons of those who discontinued.

3.8 Demographics and Baseline Characteristics

Demographic and baseline characteristics, including MDS-UPDRS Part III and BF-ADL upper limb subset scores at enrollment (Visit 1) and MDS-UPDRS Part III and BF-ADL upper limb subset scores at Visit 2b pre-stimulation, will be summarized and reported.

3.9 Effectiveness Outcomes

The effectiveness of the Cala Trio device in reducing action hand tremor symptoms in PD will be evaluated by the following:

Primary Effectiveness Endpoints

- Tremor power (kinematic response), as collected with the device during postural holds (outstretched or wing beating), change from pre-stimulation to post-stimulation across sessions. (See section 3.3 for detailed description).

This endpoint will be tested statistically using hypotheses as defined above.

Secondary Effectiveness Endpoint

- Improvements in MDS-UPDRS action tremor and BF-ADL upper limb subset scores, relevant to the stimulated upper limb, from pre- to post-stimulation (i.e., acute improvement from stimulation)
- Improvements in MDS-UPDRS action tremor and BF-ADL upper limb subset scores, relevant to the stimulated upper limb, from baseline (pre-stimulation Visit 2b) to study exit (post-stimulation Visit 3) (i.e., accumulated baseline improvement from one month therapy + acute improvement from stimulation)
- Improvements in pre-stimulation MDS-UPDRS action tremor and BF-ADL upper limb subset scores, relevant to the stimulated upper limb, from baseline (pre-stimulation Visit 2b) to last session (pre-stimulation Visit 3) (i.e., accumulated baseline improvement from one month therapy)

These endpoints will be tested statistically using hypotheses as defined above (See section 3.4 for details).

Additional Exploratory Endpoints, Clinical Data

- Raw change from pre-stimulation to post-stimulation, assessed separately for Visit 2b and Visit 3, for each of the following:
 - Per-task MDS-UPDRS Part III score
 - Per-task BF-ADL upper limb subset score
- % Subjects that had a ≥ 0.5 -point average per-task improvement in MDS-UPDRS Part III total score (six tasks, relevant to the stimulated upper limb) from pre-stimulation to post-stimulation, assessed separately for Visit 2b and Visit 3
- % Subjects that had a ≥ 0.5 -point average per-task improvement in BF-ADL upper limb subset score (nominally eight tasks, relevant to the stimulated upper limb) from pre-stimulation to post-stimulation, assessed separately for Visit 2b and Visit 3
- Per-task improvements in MDS-UPDRS Part III and BF-ADL from pre-stimulation to post-stimulation, assessed separately for Visit 2b and Visit 3 as follows:
 - Number of patients who had a pre-stimulation score ≥ 2 for that task
 - Raw change in per-task MDS-UPDRS Part III score, for the patients that had a pre-stimulation score ≥ 2 in that task
 - Raw change in per-task BF-ADL upper limb subset score, for the patients that had a pre-stimulation score ≥ 2 in that task

- Of the patients who had a pre-stimulation MDS-UPDRS score ≥ 2 for that task, % patients who had a ≥ 0.5 -point or 1-point (based on resolution of scale for that task) improvement
 - Of the patients who had a pre-stimulation BF-ADL score ≥ 2 for that task, % patients who had a ≥ 0.5 -point or 1-point (based on resolution of scale for that task) improvement
- Correlation between pre-stimulation MDS-UPDRS Part III score (average of six tasks relevant to stimulated upper limb) at Visit 2b vs Visit 3
- Correlation between pre-stimulation BF-ADL upper limb score (average of nominally eight tasks relevant to stimulated upper limb) at Visit 2b vs Visit 3
- Correlation between pre- to post-stimulation improvement in MDS-UPDRS Part III score at Visit 2b vs Visit 3.
- Correlation between pre- to post-stimulation improvement in BF-ADL upper limb subset score at Visit 2b vs Visit 3.
- Clinician/Patient Global Impression of Severity (C/PGI-S) summarized for each of Visit 2b and Visit 3
- Clinician/Patient Global Impression of Improvement (C/PGI-I) summarized for each of Visit 2b and Visit 3
- Across and within visit change in MDS-UPDRS – subset relevant to non-stimulated upper limb (raw change) (i.e., Visit 2b pre – post; Visit 3 pre – post; Visit 2b pre – Visit 3 post; Visit 2b pre – Visit 3 pre)
- Duration of effect as reported by participants (from product survey), including:
 - % of patients reporting duration of effect beyond end of stimulation
 - Descriptive statistics (mean, standard deviation, median, interquartile range) of duration of effect for the patients who reported having post-stimulation benefit)
- Summarized responses of each of the seven questions in the Product Survey

Additional Exploratory Analyses At-home

- Distribution of Patient Session Impression of Improvement (PSI-I) over the duration of the study
- Relationship between PSI-I and kinematic (tremor power) improvement
- Response at-home according to pre-stimulation tremor power severity (e.g., top 25% and 50% most severe sessions per subject), including:
 - Median kinematic improvement for each patient's high ($\geq 75^{\text{th}}$ percentile), medium ($25^{\text{th}} - 75^{\text{th}}$ percentile) and low ($\leq 25^{\text{th}}$ percentile) pre-stimulation tremor
 - Of sessions that started with patient-specific "high" tremor, % sessions that had $\geq 0\%$ and $\geq 50\%$ reduction in tremor (i.e., rate of tremor "relief")
 - Of sessions that started with patient-specific "low" tremor, % sessions that ended in "low" tremor (i.e., rate of tremor "prevention")
- Average change in tremor power 1st, 2nd, 3rd and 4th weeks
- Correlation between log-transformed median pre-stimulation tremor power in first subset of days (e.g., 7, 14) compared to analogous data from final subset of days
- Correlation between log-transformed median kinematic response in first subset of days (e.g., 7, 14) compared to analogous data from final subset of days
- Summary of available BF-ADL scores based on recall at Visit 1, and 1st, 2nd, 3rd and 4th weeks
- Device usage metrics

These exploratory endpoints will be summarized and reported descriptively. Any hypothesis testing will be performed according to the general principles defined in this document.

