2 STUDY OVERVIEW

2.1 Design and Objective

This is a prospective, single-site, single-arm, non-significant risk study designed to evaluate the Cala Trio device for action tremor in PD. Subjects will be screened for eligibility and fitted with a Cala Trio device. Subjects will wear the device at home for a period of 4 weeks, during which they will be asked to stimulate their dominant hand twice daily. The stimulation amplitude will be based on each subject's stimulation threshold. Subjects will have in-clinic assessments at enrollment, as well as before and after treatment of 4 weeks. The study timeline, reproduced from the study protocol, is illustrated below. More detail on study data follows below.

All subjects will be informed of their right to withdraw from the clinical study at any time without penalty or loss of benefits. The Investigator may prematurely discontinue any subject from the study if the Investigator feels that the subject can no longer fully comply with the requirements of the study or if any of the study procedures are deemed potentially harmful to the subject.

The study objective is to evaluate symptomatic hand tremor relief in the treated hand following stimulation with the Cala Trio device in adults with action tremor in PD over a duration of 4 weeks.

a. Visit 1

Subjects will be reminded to be in the *off* state, i.e., to skip their last dose of PD medication, prior to their telemedicine Visit 1. The following assessments will occur:

- Screening activities including medication review and medical history. No medical records will be used for this study, so all eligibility criteria will be based upon self-reported information from each subject and verification by qualified study staff.
- Tremor assessments (while in the *off* state) including:
 - Modified MDS Unified Parkinson's Disease Rating Scale Part III (MDS-UPDRS) to confirm eligibility will be rated by the PI
 - Bain & Findley Activities of Daily Living (BF-ADL) upper limb subset score will be rated by the subject based on their recall of the previous week (no props will be used)
- Demographic information, Parkinson's clinical characteristics, and wrist size and handedness will be collected based on self-reported information from subjects.

Once a subject has been confirmed to be eligible for the study, a device kit containing a stimulator, base station and band will be shipped directly to the subject's home ahead of Visit 2.

b. Visit 2

Visit 2a

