3.3 Primary Endpoint

The primary endpoint (definition below) of the study is a within-subject comparison of tremor power before stimulation to after stimulation, as captured by the Cala Trio device’s on-board accelerometer. Unless otherwise specified, “tremor frequency”, “tremor power” and “single-session kinematic response” are per-session metrics defined as follows:

- “Tremor frequency” is the frequency, in the 3 – 12 Hz range associated with Parkinson’s tremor, where the power spectral density (PSD) of a session’s pre-stimulation accelerometry data is largest.
- “Tremor power” is integral of the PSD of the tremor accelerometry data in the 3 Hz window centered on the session’s tremor frequency.

- “Single-session kinematic response” is defined as the pre-stimulation tremor power divided by the post-stimulation tremor power.

The primary endpoint, “kinematic response”, is defined as the per-patient median of single-session kinematic responses.

Patients will be included in the primary endpoint analysis only if they completed at least 10 therapeutic sessions that met the following data quality criteria:

- Session was started at least 2 hours after the completion of a previous session.
- Participant completed both pre- and post-stimulation motion recordings, that are each
 - sufficiently free of recording artifact, including accelerometer saturation
 - sufficiently free of motion artifact, as detected by excessive power outside the 3 – 12 Hz tremor range in the PSD.

Statistical testing of the primary endpoint will be based on the cohort of all enrolled subjects for whom outcome data are available. The statistical objective related to the primary endpoint is to demonstrate that action hand tremor severity in PD is reduced with the Cala Trio device. Formally, the null and alternative hypotheses to be tested for the primary endpoint is as follows:

$$H_0: M_T \geq 1$$

$$H_A: M_T < 1$$

where M_T is the median kinematic response captured over the 4-week study.

The primary endpoint is a continuous variable and will be summarized descriptively using log-transformed mean and standard deviation, median, and interquartile range (first and third quartiles). Hypothesis testing of the change score M_T will be performed using Wilcoxon’s signed-rank test.

The primary endpoint is met if the two-sided p-value is < 0.05 , such that the null hypothesis is rejected in favor of the alternative hypothesis. The study is successful if the primary endpoint is met.

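### Tiering at-home sessions by their own pre-stimulation power builds regression to the mean into the high-tier improvement, the 'relief' rates and the severity gradient

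*SAP*

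**What the plan says.** Under the at-home exploratory analyses, SAP 3.9 plans "Response at-home according to pre-stimulation tremor power severity (e.g., top 25% and 50% most severe sessions per subject), including" three outputs:

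- "Median kinematic improvement for each patient's high" (75th percentile and above), medium, and low (25th percentile and below) sessions, ranked by pre-stimulation tremor power;
- for sessions that began high, the percentage with at least 0% and at least 50% reduction, labelled the rate of 'relief';
- for sessions that began low, the percentage that ended low, labelled the rate of 'prevention'.

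SAP 3.3 defines the single-session response: it is "defined as the pre-stimulation tremor power divided by the post-stimulation tremor power". A ratio above 1 therefore means less tremor after the session. SAP 3.9 does not define kinematic improvement separately; I take it to be this ratio or a function of it.

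On design, SAP 2.1 states: "This is a prospective, single-site, single-arm, non-significant risk study". Protocol 3.7 says that neither subjects nor raters are blinded. Neither document plans untreated or sham recordings. SAP 3.9 closes by making these endpoints descriptive, with any test to follow the SAP's general principles.

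**The concern.** The variable that sorts the sessions is the numerator of the outcome. A session enters the high tier partly because tremor happened to be high at that moment, and the next recording will tend to lie closer to the patient's usual level whether or not stimulation does anything. The ratio is then above 1 in the high tier and, by the same mechanism, below 1 in the low tier.

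These outputs describe when the device helps at home, and two of them carry treatment-effect names. A reader who sees most high sessions improving, and more benefit when tremor starts worse, would take both as properties of the device. Part or all of either can come from the sorting, and SAP 3.9 gives no reference value to show how much. More subjects or sessions do not remove the bias.

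**Working it through.** The plan states no figure for the tiered analysis, so there is nothing to reproduce. The check asks what the planned outputs look like when stimulation does nothing.

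**Inputs from the documents.** Tiers cut at each patient's own 25th and 75th percentiles of pre power (SAP 3.9). Response = pre/post (SAP 3.3). Planned sessions: 2 per day × 28 days = 56 (Protocol 3.17). Analysis size: 34 to 50 subjects (SAP 3.6); I use 40. Minimum for the primary analysis: 10 usable sessions (SAP 3.3).

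**Assumptions (not in the documents).** Log pre and log post power are normal within subject, with equal means, equal SD s (0.5 or 1.0) and correlation r (0.3 to 0.9).

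**Formula.** With no effect,

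E[log pre − log post | pre] = (1 − r)(log pre − mean).

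This is positive in the high tier and negative in the low tier for any r < 1. The mean of a standard normal above its 75th percentile is 0.3178/0.25 = 1.271, so the high-tier ratio is roughly exp{(1 − r) × s × 1.271}. For r = 0.5 and s = 0.5 that is exp(0.318) = 1.37. For r = 0.9 and s = 0.5 it is exp(0.0636) = 1.07.

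**Simulation, no effect, 40 subjects × 56 sessions** (per-patient tier median, then summarised over patients):

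| r | s | High | Medium | Low | ≥ 0% reduction, high | ≥ 50% reduction, high |
|---|---|---|---|---|---|---|
| 0.3 | 0.5 | 1.54 | 1.00 | 0.65 | 80% | 31% |
| 0.5 | 0.5 | 1.37 | 1.00 | 0.73 | 76% | 20% |
| 0.7 | 0.5 | 1.21 | 1.00 | 0.83 | 70% | 8.5% |
| 0.9 | 0.5 | 1.07 | 1.00 | 0.94 | 61% | 0.2% |
| 0.3 | 1.0 | 2.4 | 1.00 | 0.42 | 81% | 57% |
| 0.5 | 1.0 | 1.86 | 1.00 | 0.54 | 76% | 47% |
| 0.7 | 1.0 | 1.45 | 1.00 | 0.69 | 70% | 33% |
| 0.9 | 1.0 | 1.13 | 1.00 | 0.88 | 61% | 10% |

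The 'prevention' rate under no effect runs from 39% (r = 0.3) to 77% (r = 0.9), so it too has no obvious reference value.

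**If a test were run.** A signed-rank test of the high-tier medians against a ratio of 1 favours benefit in 99.7% to 100% of these null trials. With 34 subjects at the 10-session minimum it does so in about 94% to 98% at r = 0.7, but only about half at r = 0.9.

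**With a uniform non-specific fall of 1.2-fold** (r = 0.9, s = 0.5), each tier is multiplied by 1.2: high 1.07 × 1.2 = 1.28, medium 1.20, low 0.94 × 1.2 = 1.13. The low tier no longer worsens; the high tier is still inflated relative to 1.20.

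**The mirror.** Take sessions in the top quartile of post power and compute post/pre. With no effect and equal variances this equals the high-tier value, so the log difference is zero. Under the 1.2-fold fall the mirror is 1.07/1.2 = 0.89. High divided by mirror is 1.28/0.89 = 1.44 = 1.2², so the raw excess counts the shift twice. Half the log difference gives √1.44 = 1.20, the true value.

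**Where the mirror fails.** Let the post SD be k × s. The expected half log difference is then s × 1.271 × (1 + r)(1 − k)/2 with no shift. For k = 0.9 it is 0.5 × 1.271 × 1.5 × 0.05 = 0.048 (ratio 1.05) at r = 0.5, s = 0.5, and 1 × 1.271 × 1.9 × 0.05 = 0.121 (ratio 1.13) at r = 0.9, s = 1.0. The residual bias is modest in size, but in simulation with k = 0.9 both the mirror contrast and tiers on the geometric mean of pre and post showed false benefit in 77% to 100% of trials.

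**The case against.** The strongest reply is that nothing decisive rests on this. The analyses are exploratory and descriptive, no test of the tiers is named, the primary endpoint uses the median over all qualifying sessions, and the secondary hierarchy never uses tiers. All of that stands, and it limits the harm to interpretation. It does not remove the point, because this is a one-directional bias rather than noise, and the outputs are labelled relief and prevention.

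Three stronger readings are tempting, and the documents do not support them.

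- *The tiered analyses cannot tell a working device from an inert one.* SAP 3.9 also requires the medium tier, which reads 1.00 under no effect and 1.20 under a uniform 1.2-fold fall. Read together, the three tiers do separate an overall shift from none. What misleads is the high tier, the relief rates or the gradient read alone.
- *The low tier always shows worsening.* That needs no overall pre-to-post fall. A non-specific fall is plausible in an unblinded single-arm study, and can lift the low tier above 1.
- *Any test would be significant.* With few usable sessions and high correlation, a high-tier test rejects only about half the time.

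It is also fair to say that size depends on two quantities the documents do not give: the rate of at least 50% reduction runs from 0.2% to 57%. The direction is established; the practical size is not.

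Finally, neither correction is free of assumptions. SAP 3.3 takes the tremor frequency from the pre-stimulation recording and centres the power window there, which may itself break the symmetry between pre and post. That limits how exactly the correction works, not the diagnosis.

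**Conclusion.** The point holds as one of interpretation. Because SAP 3.9 tiers on the numerator of the SAP 3.3 response, the high-tier improvement and relief rates are inflated, the low tier is deflated, and a severity gradient appears without any effect. For 40 subjects and 56 sessions, an inert device would give high-tier ratios of about 1.07 to 2.4, low-tier ratios of about 0.94 to 0.42, and some reduction in 61% to 81% of high sessions. These sizes rest on assumed correlations of 0.3 to 0.9, log SDs of 0.5 to 1.0, equal pre and post variance and no overall shift. The mechanism itself needs only that pre and post power are imperfectly correlated.

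A reader might infer that the study's main result is compromised. It is not: the primary and secondary endpoints do not use the tiers. The change is worth making before the at-home results are reported, but the trial does not depend on it.

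**What to change.** In SAP 3.9:

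1. Keep the tiers. Beside each high-tier median and each relief rate, print its mirror image: sessions in the patient's top quartile of post-stimulation power, with the response computed as post/pre. For the relief rates, the mirror serves as the no-effect reference.
2. Read a high-tier effect only from half the log difference between the high-tier median and its mirror, so that a uniform shift is not counted twice.
3. Give tiers on the per-session geometric mean of pre and post power as a sensitivity analysis. These no longer describe how the session started, so they should not replace the planned tiers.
4. Present and interpret the high, medium and low tiers together.
5. State that both corrections assume equal within-subject variance of log pre and log post power, and report those variances.
6. State that neither correction separates stimulation from a non-specific pre-to-post fall.

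The cost is a few lines of SAP text and a little more analysis, with no new data. The relief figures will look less favourable beside their reference.

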3.10 Subgroup and Covariate Analysis

Primary and secondary endpoints will be investigated for each of the following subgroups:

- Gender (M/F)
- Age (< 65 vs. \geq 65 years)
- Age onset of hand tremor in PD (by median split)
- Duration of PD from beginning of tremor symptom (by median split)
- Tremor Medications (On/Off)
- Antidepressant medications (On/Off)
- Preset Stimulation amplitude (by median split)
- Average Final Stimulation amplitude (by median/mean split)
- Stimulation calibration frequency (by median split)
- Baseline tremor severity as measured by UPDRS (by median split)
- Baseline tremor severity as measured by BF-ADL scale (by median split)
- Pre-stimulation tremor power, aggregated over first week (by median split)

Comparisons within subgroups will be performed using the same statistical tests as specified above for the overall cohort.

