3 STATISTICAL METHODS

3.1 General Principles

- All hypothesis testing will be performed using a two-sided test at a 0.05 level of significance or a one-sided test at a 0.025 level of significance. Significance levels will be adjusted for multiple hypothesis testing where appropriate. P-values will be reported as raw uncorrected p-values and rounded to three decimal places. If a p-value is less than 0.001 it will be reported as “< 0.001.”
- Summary statistics will be reported for all analyzed variables.
 - Continuous data will be summarized using descriptive statistics appropriate for the underlying data distribution, e.g., mean, standard deviation, median, and interquartile range (first and third quartiles).
 - Categorical, non-ordered variables will be summarized using frequency counts and percentages.
 - Ordinal variables, including those specific to study outcomes – e.g., the modified Movement Disorder Society Unified Parkinson’s Disease Rating Scale (MDS-UPDRS) Part III and the Bain & Findley Activities of Daily Living (BF-ADL) scale – will be summarized using measures of central tendency and variance as opposed to frequency counts and percentages; that is, these variables will be reported using the same metrics as defined above for continuous variables.
- For events which can occur more than once in a single subject (e.g., adverse events), the percentage will be based on number of subjects experiencing the event, and both subject and event counts will be reported.
- Baseline is defined as the last measurement for the outcome of interest obtained before the exposure to study treatment.
- For time-to-event analyses, complete dates for events of interest (e.g., index treatment, outcome events, censoring), will always be used. Incomplete dates will be incorporated by defining the event as occurring on the earliest date possible given the incomplete information. E.g., a date of UNK-FEB-2018 will be incorporated into the analysis as 01-FEB-2018.
- Statistical analyses will be performed in SAS (SAS Institute, Cary, N.C.) version 9.3 or later, R (R Foundation for Statistical Computing, Vienna, Austria) version 3.2 or later,

Matlab (The MathWorks, Inc., Natick, MA) version R2016B or later, Python (Anaconda, Inc., Austin, TX) version 3.6.6 or later, or in another validated statistical software package.

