The secondary endpoints will be summarized descriptively using mean, standard deviation, median, first and third quartiles, and interquartile range (between first and third quartiles). Hypothesis testing of the mean change score (μ_T) will be performed using one-sample t-tests (equivalent to a two-sample paired test). Formally, the null and alternative hypotheses to be tested for each of the secondary endpoints are as follows:

$$H_0: \mu_T = 0$$

$$H_A: \mu_T \neq 0.$$

Secondary endpoints will only be tested for statistical significance if the primary endpoint is met. Secondary endpoints will be tested in a hierarchical stepwise manner, using a fixed sequence procedure: 1a -1d first, 2a and 2b second, and 3a and 3b third. Statistical significance level will be set at $p < 0.05$ for each of the three endpoint groups, with group 2 (2a, 2b) only tested if all tests in group 1 (1a – 1d) meet significance, and group 3 (3a, 3b) only tested if group 2 meets significance. Because all endpoints within a step (e.g., endpoints 1a – 1d in endpoint group 1) must meet the two-sided $p < 0.05$ in order to proceed to the next step, no adjustment for multiplicity is required.

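### SAP 3.10 appears to split the severity subgroups on the score from which six secondary changes are measured, so regression to the mean will look like benefit in the severe half

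*SAP*

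**What the plan says.** SAP 3.10 names two severity subgroups, "Baseline tremor severity as measured by UPDRS (by median split" and "Baseline tremor severity as measured by BF-ADL scale (by median split", and then states: "Comparisons within subgroups will be performed using the same statistical tests as specified above for the overall cohort". For the secondary endpoints that test comes from SAP 3.4: "Hypothesis testing of the mean change score (μ_T) will be performed using one-sample t-tests (equivalent to a two-sample paired test", with a null value of zero mean change.

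The general definition in SAP 3.1 is "Baseline is defined as the last measurement for the outcome of interest obtained before the exposure to study treatment". SAP 3.9 places it at a visit when it describes the four-week change as running "from baseline (pre-stimulation Visit 2b) to study exit (post-stimulation Visit 3".

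In SAP 3.4, endpoints 1a, 1c, 2a, 2b, 3a and 3b all start from the Visit 2b pre-stimulation score. Endpoints 1b and 1d start from the Visit 3 pre-stimulation score.

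Two things are left open. SAP 3.10 names neither a visit nor a task set for the split. SAP 3.8 lists, as baseline characteristics, both "MDS-UPDRS Part III and BF-ADL upper limb subset scores at enrollment (Visit 1" and the Visit 2b pre-stimulation scores.

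**The concern.** A rating is a true level plus error on the day. Subjects placed in the upper half by the Visit 2b pre-stimulation rating were, on average, rated above their usual level on that occasion. Any later rating tends to fall back, and the difference counts as improvement. The lower half does the reverse. Zero mean change is the no-effect value for the whole cohort, but not within either half. The study has one arm, so no control group shows how much of the change is this artefact.

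Each split acts directly on the three endpoints of its own scale: 1a, 2a and 3a for UPDRS, and 1c, 2b and 3b for BF-ADL. At stake is the reading of the subgroup tables that SAP 3.5 says will be reported. A device that appears to help severe tremor and not mild tremor is clinically plausible, and this split tends to produce that pattern by itself. Correcting for multiplicity, or testing the halves against each other, would not remove it.

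**Working it through.** **Inputs from the documents.** Two-sided 0.05, so 2.5% in the benefit direction (SAP 3.1). N from 34 to 50 (SAP 3.6), so n = 17 to 25 per half. One-sample t-test against 0 (SAP 3.4).

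**Assumption.** The correlation r between repeated ratings with no device effect is not given. The range used is 0.6 to 0.95.

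**Step 1: the plan's own level.** With no effect and no split, simulation (true score plus independent error on each occasion, 20,000 trials per setting) rejected for benefit in 2.3% to 2.7% of trials, and two-sided in 4.8% to 5.3%. The test holds its level in the whole cohort.

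**Step 2: the shift caused by the split.** With ratings scaled to SD 1, the mean of the upper half is √(2/π) = 0.798. Within that half, under no effect:

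- mean change = (1 − r) × 0.798
- variance of change = (1 − r)² × (1 − 2/π) + 1 − r²

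At r = 0.8 the mean is 0.2 × 0.798 = 0.160 and the variance is 0.04 × 0.363 + 0.36 = 0.3745. The standardised shift is 0.160/√0.3745 = 0.261. With n = 25 the noncentrality is 0.261 × 5 = 1.30 and the critical t is 2.064, giving 23.9% false benefit. With n = 17 it is 17.1%.

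**Step 3: false benefit in the severe half, split on Visit 2b pre-stimulation (nominal 2.5%), simulated.**

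| r | N=34 | N=50 |
|---|---|---|
| 0.6 | 30.5% | 44.2% |
| 0.7 | 23.8% | 33.8% |
| 0.8 | 16.6% | 23.4% |
| 0.9 | 10.5% | 13.5% |
| 0.95 | 6.9% | 8.4% |

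The formula agrees within about one percentage point. The mild half shows false worsening at about the same rates. Endpoint 1b stays at 2.2% to 2.7%, which isolates the shared starting value as the cause; 1d behaves the same way by construction.

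**Step 4: coarse ratings.** With two integer 0–4 items averaged, the Visit 1 entry cut of 2 and ties at the median, the rates by observed correlation are as follows (ranges: ties included or excluded).

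| Observed r | N=34 | N=50 |
|---|---|---|
| 0.86 | 9.6–12.0% | 12.9–16.7% |
| 0.80 | 14–16% | 19–24% |
| 0.69 | 21–27% | 29–39% |

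**Step 5: which r applies to which endpoint.** Endpoints 1a and 1c compare ratings on either side of one 40-minute session, so r is probably high. At a within-visit r of 0.90 to 0.95, the rate for 1a is about 7% to 11% at N=34 and 8% to 14% at N=50. Endpoints 2a, 2b, 3a and 3b span four weeks and follow the lower between-visit r.

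**Step 6: splitting on Visit 1 instead.** With independent errors on each occasion, the severe-half rate for 1a returns to 2.3% to 2.6%. If correlation decays with time, some bias remains in the four-week changes. Let a be the correlation of Visit 1 with Visit 2b, c that of Visit 1 with Visit 3, and b that of Visit 2b with Visit 3. The mean change is (a − c) × 0.798, and the variance is 2(1 − b) − (a − c)² × 2/π.

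- a = 0.75, b = c = 0.6: mean 0.120, variance 0.786, false benefit 7.6% (n = 17) and 9.5% (n = 25).
- a = 0.88, b = c = 0.8: mean 0.064, variance 0.396, false benefit 5.9% and 7.0%.

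**The case against.** **The visit is inferred.** SAP 3.10 names none, SAP 3.8 lists Visit 1 scores too, and the Visit 2b label in SAP 3.9 describes the change scores, not the split. Stimulation intensity is set at Visit 2a. If that counts as exposure and 2a is held separately, the last rating before exposure would be Visit 1. This stands as a caveat. Visit 2b is still the natural reading, because SAP 3.9 calls it baseline for these very scores. If Visit 1 was intended, SAP 3.10 should say so.

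**The split may use another score.** SAP 3.9 uses a six-task Part III average elsewhere, while the secondary endpoint averages two action-tremor tasks. A six-task split would weaken the coupling. It would not remove it, since the six include those two.

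**The size rests on an assumed r.** This is correct. The effect is modest at 0.95 and vanishes as r approaches 1.

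**The results decide nothing.** Study success depends on the primary endpoint alone (SAP 3.3), and secondary tests follow only if it is met (SAP 3.4). This limits the consequence. But SAP 3.10 does not say whether that condition binds the subgroup tests, and it does not correct the rate of any test that is run.

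**Visit 1 is not a perfect substitute.** This also stands, and the remedy has to allow for it.

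**Conclusion.** The concern holds, with limits. If the splits use the Visit 2b pre-stimulation value of the endpoint's own score, the within-half t-tests of 1a, 2a and 3a (UPDRS split) and 1c, 2b and 3b (BF-ADL split) do not hold their level. For r from 0.6 to 0.95, false benefit in the severe half is about 31% to 7% at N=34 and 44% to 8% at N=50, against 2.5%; repeat simulations differ by about a point. The pre-to-post changes within a visit probably lie at the low end, and the four-week changes higher.

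A reader might infer more than this. The documents do not support the following:

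- That the primary result or study success is compromised. Neither depends on these subgroups, and 1b and 1d do not share the starting value.
- That one split distorts six of the eight secondary endpoints. Each acts directly on three.
- That the findings would shape labelling. Nothing in the documents gives them that role.
- That the higher rates apply to every affected endpoint. That would need a low correlation even across one 40-minute session.

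**What to change.** In SAP 3.10, define the two severity splits on the Visit 1 scores: the MDS-UPDRS action-tremor average (postural and kinetic) for the stimulated limb, and the BF-ADL recall score. Keep the Visit 2b pre-stimulation score only as the starting value of the changes.

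Add a sentence that within-half changes in 2a, 2b, 3a and 3b may still carry some regression to the mean and are descriptive. The residual false benefit is about 6% to 10% if ratings a week apart correlate more than ratings five weeks apart. The within-visit endpoints 1a and 1c return to about the nominal level.

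The cost is two sentences and no new data. The downside is that the split measures severity somewhat differently. Visit 1 postural scores are truncated at 2 by the entry rule, and the Visit 1 BF-ADL is recalled over a week without props, whereas the Visit 2b score is performed with household props.
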